The occurrence of AEs (serious and non-serious) will be assessed by non-directive questioning of the subject at each visit. AEs volunteered by the subject during or between visits as subject diary card entries or detected through observation, physical examination, laboratory test, or other assessments during the entire trial, will be documented. Subjects will be instructed that they must immediately report any AEs with serious symptoms, subjective complaints or objective changes in their well-being to the investigator or the clinic personnel, regardless of the perceived relationship between the event and the test vaccine.

SAEs, MAAEs and AEs leading to trial or vaccine withdrawal will be collected up to 12 months after the last dose administration. After Visit 15 (Month 12), only SAEs and MAAEs that according to the investigator are considered to be related to study vaccination will be collected.

Intercurrent medical conditions and AESIs will be collected throughout the trial.

Clinical laboratory testing for safety evaluations are provided in Appendix 6. Definitions and procedures for recording, evaluating, follow-up and reporting of AEs are provided in Appendix 11.

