Visit 15A may be conducted only in case Visit 15 was conducted as a phone call, and when restrictive measures related to COVID-19 no longer prevent site visits, and the window of Visit 15 has expired. Visit 15A allows the trial procedures, including the blood draws for safety and immunogenicity testing, to occur during a widened visit window starting the day after the expiry of the original visit window and lasting up to 3 months after the original projected visit date (+31-90 days). In that case, all procedures as described in Section 9.4.17.1 for Visit 15, including and blood sampling for safety and immunogenicity assessments, should be performed at Visit 15A.

Also, in case Visit 15 was conducted on site but not all procedures could be performed, Visit 15A should be scheduled on site within the protocol-allowed time interval for Visit 15A (+31-90 days).

If no blood sampling could be performed at Visit 15 and 15A, the end-of-trial blood sample for safety assessment may be performed at Visit 17 (Month 24: Day 729).

9.4.18 *Visit 16 (Month 18: Day 547)*

9.4.18.1 *Visit 16*

The following activities will be performed during Visit 16:

- Safety assessments (SAEs related to study vaccination, MAAEs related to study vaccination, intercurrent medical conditions, AESIs and concomitant medications and vaccinations).
- Blood draw for immunogenicity (only in subjects with detectable RABV-G-specific IgG at 6 months after the last vaccination or Day 91 if the Month 6 blood sample is not available) – VNTs (~18 ml), IgG (~6 ml) (section 9.5.3).

In case Visit 16 cannot take place on site due to the public health emergency related to COVID-19, safety information should be collected via a phone call within the protocol-allowed time interval for Visit 16 (± 30 days).

9.4.18.2 *Optional Visit 16A*

Visit 16A may be conducted only in case Visit 16 was conducted as a phone call, and when restrictive measures related to COVID-19 no longer prevent site visits, and the window of Visit 16 has expired. Visit 16A allows the trial procedures, including the blood draws for immunogenicity testing, to occur during a widened visit window starting the day after the expiry of the original visit window and lasting up to 3 months after the original projected visit date (+31-90 days). In that case, all procedures as described in

Section 9.4.16.1 for Visit 16, including blood sampling for immunogenicity assessment, should be performed at Visit 16A.

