[REDACTED]
[REDACTED]
[REDACTED]
[REDACTED]

- In rare circumstances and in the absence of email or facsimile equipment, notification by telephone is acceptable with a copy of the SAE data collection tool sent by overnight mail or courier service.
- Initial notification via telephone does not replace the need for the investigator to complete and sign the SAE report form within the designated reporting time frames.
- The “**initial SAE report**” should be as complete as possible, including causality assessment, details of the current illness and (S)AE, the reason why the event was considered serious; date of onset and end date (if applicable); diagnostic procedures and treatment of the event; relevant medical history and concomitant medication and vaccinations; and action taken with trial vaccine. The SAE report form must be signed by the investigator or his authorized designee(s).
- Investigator must inform [REDACTED] about AESIs and cases of overdose by applying the same timelines and rules of SAEs reporting.

Determination of Expectedness, Reference Safety Information

- Expectedness will be determined by [REDACTED] according to the designated Reference Safety Information (RSI) provided in the current IB. Any updates or substantial amendments will be considered accordingly.

Observation Period

- For the purpose of this trial, the period of observation for collection of AEs extends from the time the subject gives informed consent until the end of the trial.
- All AEs that occur in the course of the clinical trial regardless of the causal relationship should be monitored and followed up until the outcome is known or it is evident that no further information can be obtained.
- There must be documented reasonable attempts to obtain follow-up information and outcome.
- It is the responsibility of the investigator to ensure that any necessary additional therapeutic measures and follow-up procedures are performed.

Post-Trial Events

- If the investigator becomes aware of any SAE that occurred after the end of the trial but is considered to be caused by the trial vaccine(s), this must be reported to [REDACTED].
- These SAEs will be processed by [REDACTED]. Instructions for how to submit these SAEs will be provided in a handout in the Investigator Site File.

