11.1 Safety Endpoints and Variables

The analysis of the primary objective to assess the safety and reactogenicity profile will examine solicited and unsolicited adverse events.

The primary endpoints include the following:

- The percentages of subjects with, and the frequencies and intensities of solicited local AEs reported on the day of vaccination and the 7 subsequent days (Days 1-8).
- The percentages of subjects with, and the frequencies, intensities, and relationship to vaccination of solicited systemic AEs reported on the day of vaccination and the 7 subsequent days (Days 1-8).
- The duration (in days) of solicited local AEs, of solicited systemic AEs, and of the individual solicited AEs.
- The percentages of subjects with and frequencies and intensities of any unsolicited and related unsolicited AEs reported on the day of vaccination and the 28 subsequent days (Days 1-29).

- The percentages of subjects with and frequencies and relationship to vaccination of any serious AEs (SAEs) and any medically attended AEs (MAAEs) up to 12 months after the last dose.
- The percentages of subjects with and frequencies and relationship to vaccination of any AEs of special interest (AESIs) up to 12 months after the last dose.

Secondary safety endpoints are:

- The percentages of subjects with and frequencies of SAEs and MAAEs related to study vaccination from 12 months after the last dose up to 24 months after the last dose (trial end).
- The percentages of subjects with and frequencies and relationship to vaccination of any AESIs from 12 months after the last dose up to 24 months after the last dose (trial end).

Further safety variables include the following:

- Extent of exposure
- Physical examination, weight, BMI
- 12-Lead electrocardiogram
- Vital signs
- Safety laboratory - hematology, biochemistry, coagulation
- Laboratory - Urine dipstick pregnancy test, serum pregnancy test (human chorionic gonadotropin)

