11.2.2 Unsolicited Adverse Events

Serious AEs, intercurrent medical conditions, AEs leading to trial or vaccine withdrawal, AEs of special interest (AESIs) and MAAEs will be collected by the investigator in the eCRF throughout the trial.

AEs with a suspected potential immune-mediated disease etiology will be considered AESIs. The investigator will assess if an AE is an AESI. A list of AESIs is provided in Appendix 10 of the protocol.

AEs that are reported as related to the test vaccine will be considered trial vaccine-related; missing classifications concerning trial vaccine relationship will also be considered trial vaccine-related.

Every unsolicited AE will be assigned to a vaccination dose (number) by consideration of the period of 28 days after vaccination administration. Unsolicited AEs can be assigned to either day 1 to 28 (dose 1 for any vaccination group), or day 29 to 57 (dose 2 for 2-dose regimens or dose 3 for the Rabipur group). For the Rabipur group, vaccination dose 2 is administered 8 days after vaccination dose 1, therefore no assignment of unsolicited AEs to vaccination dose 2 is done for the Rabipur group.

All AE summaries will be restricted to those AEs that occurred after the first administration of the trial product. Any other AE (ie, AE starting after trial entry and before the first vaccination) will be reflected only in the data listings. If it cannot be determined whether the AE occurred after the first administration of the trial product due to a partial onset date, then it will be counted as such. Verbatim terms in the eCRFs will be mapped to preferred terms (PTs) and system organ classes (SOCs) using the Medical Dictionary for Regulatory Activities (version 21.0 or higher).

The occurrence of unsolicited AEs reported on the day of vaccination and the 28 subsequent days will be presented. In addition selected AE summary tables will be repeated for unsolicited AEs occurring at any time after the first administration of the trial product.

Each AE summary will be displayed by vaccination group and dose regimen. Summaries by vaccination dose (number) will also be provided for all AEs. Summaries that are displayed by SOC and PT will be ordered by descending order of incidence of SOC and PT within each system organ class. Summaries will display number and percentage of subjects with at least 1 event and the number of events by vaccination group.

Summaries of the following types will be presented:

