Preferred term 4	xx (xx.x%) xxx	xx (xx.x%) xxx	xx (xx.x%) xxx	xx (xx.x%) xxx
...	xx (xx.x%) xxx	xx (xx.x%) xxx	xx (xx.x%) xxx	xx (xx.x%) xxx
System organ class 2	xx (xx.x%) xxx	xx (xx.x%) xxx	xx (xx.x%) xxx	xx (xx.x%) xxx
Preferred term 1	xx (xx.x%) xxx	xx (xx.x%) xxx	xx (xx.x%) xxx	xx (xx.x%) xxx
Preferred term 2	xx (xx.x%) xxx	xx (xx.x%) xxx	xx (xx.x%) xxx	xx (xx.x%) xxx
Preferred term 3	xx (xx.x%) xxx	xx (xx.x%) xxx	xx (xx.x%) xxx	xx (xx.x%) xxx
...	xx (xx.x%) xxx	xx (xx.x%) xxx	xx (xx.x%) xxx	xx (xx.x%) xxx

n = Number of subjects; m = Number of events;

AEs on the day of vaccination and 28 subsequent days.

Adverse events were coded using MedDRA version 24.1. At each level of summation (system organs class, preferred term) subjects reporting more than 1 event are included only once.

Table is sorted by descending subject count in the total column by system organ class and preferred term.

Percentages are based on total number of subjects in each vaccination group

PROGRAM SOURCE: tlif-###, DATA CUT OFF DATE: DDMMYYYY

RUN DATE: DDMMYYYY hh:mm

Programming note:

Sort by decreasing frequency of the total column by SOC and preferred term.

According to the SAP all unsolicited AE tables will be restricted to adverse events that occurred AFTER the first administration of the trial vaccine (post vaccination). If adverse events BEFORE are documented, they will be flagged and listed only.

Sponsor

Clinical Study Report

Page x of y

Protocol number

14.3.1.3.1 Overall Summary of Unsolicited Adverse Events for the Duration of the Trial After any Dose, Safety Analysis Set

Adverse Event Category [n (%) m]	CV7202 1 µg (N = xx)	CV7202 2 µg (N = xx)	CV7202 5 µg (N = xx)	Rabipur (N = xx)
All unsolicited adverse events	xx (xx.x%) xxx	xx (xx.x%) xxx	xx (xx.x%) xxx	xx (xx.x%) xxx
Related unsolicited adverse events	xx (xx.x%) xxx	xx (xx.x%) xxx	xx (xx.x%) xxx	xx (xx.x%) xxx
Serious adverse events	xx (xx.x%) xxx	xx (xx.x%) xxx	xx (xx.x%) xxx	xx (xx.x%) xxx
Related serious adverse events	xx (xx.x%) xxx	xx (xx.x%) xxx	xx (xx.x%) xxx	xx (xx.x%) xxx
Medically attended adverse events	xx (xx.x%) xxx	xx (xx.x%) xxx	xx (xx.x%) xxx	xx (xx.x%) xxx
Adverse events leading to withdrawal from study	xx (xx.x%) xxx	xx (xx.x%) xxx	xx (xx.x%) xxx	xx (xx.x%) xxx
Adverse events leading to discontinued vaccination	xx (xx.x%) xxx	xx (xx.x%) xxx	xx (xx.x%) xxx	xx (xx.x%) xxx
Adverse events of special interest	xx (xx.x%) xxx	xx (xx.x%) xxx	xx (xx.x%) xxx	xx (xx.x%) xxx

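### SAP 11.2.2 says SAEs, MAAEs and withdrawal AEs are collected throughout the trial, but after Month 12 the protocol collects only vaccine-related SAEs and MAAEs, so the trial-long AE tables mix two collection rules without a label

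*SAP*

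**What the plan says.** **SAP 11.2.2.** The sentence on collection opens with "Serious AEs, intercurrent medical conditions, AEs leading to trial or vaccine withdrawal" and ends "AESIs) and MAAEs will be collected by the investigator in the eCRF throughout the trial". It makes no distinction by time or relatedness.

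**Protocol 9.2.** "SAEs, MAAEs and AEs leading to trial or vaccine withdrawal will be collected up to 12 months after the last dose administration". After Visit 15, "only SAEs and MAAEs that according to the investigator are considered to be related to study vaccination will be collected". Intercurrent conditions and AESIs are collected for the whole trial. The synopsis and section 10.3.5 repeat this rule.

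**Protocol 9.4.18 and 9.4.19 (Visits 16 and 17).** Both list "Safety assessments (SAEs related to study vaccination, MAAEs related to study vaccination, intercurrent medical conditions, AESIs" and concomitant medications and vaccinations. AEs leading to withdrawal, listed at every visit from Visit 3 to Visit 15, are no longer there. Note m to Table 2.1 agrees: before Month 18, related SAEs and MAAEs were captured within all SAEs and MAAEs.

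**SAP 11 and 11.1.** Section 11 refers to Protocol 9.2 for collection. Section 11.1 has a primary endpoint of any SAE and any MAAE up to 12 months after the last dose, and a secondary endpoint of "frequencies of SAEs and MAAEs related to study vaccination from 12 months after the last dose up to 24 months".

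**Passages pointing the other way.** Protocol Appendix 11, under Observation Period, says "the period of observation for collection of AEs extends from the time the subject gives informed consent until the end of the trial". Protocol 9.2 itself also says that AEs volunteered or detected at any time in the trial are documented.

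**Tables.** SAP Appendix C has two windows for unsolicited AEs: 28 days after vaccination, and the whole trial. The main trial-long shell is "14.3.1.3.1 Overall Summary of Unsolicited Adverse Events for the Duration of the Trial After any Dose, Safety Analysis Set".

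**The concern.** The SAP describes the second-year data as complete when, under the protocol's specific rule, they are not. A programmer or report author working from SAP 11.2.2 would have no reason to treat the year after Month 12 differently, and the shells do not prompt it.

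Shell 14.3.1.3.1 would then put events collected under two rules into one row. A reader would take the SAE and MAAE rows as what happened over two years. They would in fact show everything reported in the first year plus mainly vaccine-related events in the second. The MAAE row cannot be separated by eye, because the shell has no related-MAAE row.

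The windows that SAP 11.1 names for its primary and secondary SAE and MAAE endpoints (to Month 12, and Month 12 to 24) have no summary table in Appendix C. The nearest table answers neither.

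**Working it through.** The documents state no figure to reproduce here, so the check has three parts.

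**1. Collection rule by event type, before and after Visit 15**

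| Event | SAP 11.2.2 | Protocol 9.2 to Month 12 | Protocol 9.2 and Visits 16–17, after Month 12 |
|---|---|---|---|
| SAEs | all, whole trial | all | related only |
| MAAEs | all, whole trial | all | related only |
| AEs leading to withdrawal | all, whole trial | all | not listed |
| AESIs, intercurrent conditions | whole trial | all | all |

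The first three rows conflict and the fourth does not. The secondary endpoint in SAP 11.1 agrees with the last column, so SAP 11.2.2 also disagrees with the SAP itself.

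**2. Which tables are affected**

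- 14.3.1.3.1 has rows for all unsolicited AEs, related AEs, SAEs, related SAEs, MAAEs, AEs leading to study withdrawal, AEs leading to discontinued vaccination, and AESIs. Its footnote pools the day of vaccination and all later days. Percentages are based on subjects in the group.
- 14.3.1.3.2 shows all and related unsolicited AEs by maximum grade. 14.3.1.3.3 to 14.3.1.3.5 are system organ class and preferred term tables. None has SAE, MAAE or withdrawal rows, but their all-AE counts span the same mixed window.
- The all-unsolicited counts mix windows for a second reason: other unsolicited AEs are collected only on the day of vaccination and the 28 days after it (Protocol 9.1).

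**3. How much follow-up is under the restricted rule**

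Inputs from the notes to Protocol Table 2.1: Month 12 is Day 365 (one dose) or Day 393 (two doses and Rabipur); Month 24 is Day 729 for all.

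- One dose: (729 − 365)/(729 − 1) = 364/728 = 50.0%.
- Two doses and Rabipur: (729 − 393)/(729 − 1) = 336/728 = 46.2%.

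SAP 6.4 gives 53 vaccinated subjects. With 8 of each 16 receiving a second dose, 8 + 8 + 10 = 26 are one-dose, and 8 + 8 + 11 = 27 are two-dose or Rabipur. With no dropout:

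- To Month 12: (26 × 364 + 27 × 392)/365.25 = 54.9 person-years.
- Month 12 to 24: (26 × 364 + 27 × 336)/365.25 = 50.7 person-years.
- Restricted share: 50.7/105.6 = 48%.

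**Illustration only.** The documents give no event rates. Assume constant rates per subject-year, *u* for unrelated and *r* for related events, with no unrelated event captured after Month 12 by any route. Then the full count is (*u* + *r*) × 105.6 and the count shown is *u* × 54.9 + *r* × 105.6.

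| *u* | *r* | Full count | Shown | Missing |
|---|---|---|---|---|
| 0 | any | equal | equal | 0% |
| 0.02 | 0.05 | 7.4 | 6.4 | 14% |
| 0.1 | 0.05 | 15.8 | 10.8 | 32% |
| 0.5 | 0.05 | 58.1 | 32.7 | 44% |
| 1.0 | 0.01 | 106.7 | 55.9 | 48% |

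The related count, *r* × 105.6, is the same in both columns. Only the all-cause total falls.

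**The case against.** The best case for leaving the plan alone is that the SAP already contains the right rule: section 11 defers to Protocol 9.2 and section 11.1 states both endpoint windows correctly. No endpoint asks for a 24-month all-cause incidence. The trial is descriptive, and the AE listing gives start dates and relationship, so a careful reader could rebuild either window. All of this is true, and it limits the weight of the point. It does not remove it, because the summary table that will be read is the pooled one, and Appendix C has no table for the windows the endpoints name.

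Four stronger readings are tempting, and the documents do not support them.

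- *The tables inflate the related share.* No shell prints a related-to-all ratio. A reader could form one for SAEs from adjacent rows, and it would be too high if unrelated SAEs were lost. For MAAEs the shell has no related row from which to form it.
- *Late withdrawal AEs show as zero.* Not necessarily. A withdrawal caused by a related SAE, a related MAAE, an AESI or an intercurrent condition can still be recorded, and the disposition tables give adverse event as a reason for termination. The row for discontinued vaccination loses nothing, since the last planned dose is on Day 29.
- *All unrelated second-year events disappear.* Some can enter as AESIs or intercurrent conditions. The AE listing shell has an intercurrent field beside those for AESI and MAAE.
- *Protocol 9.2 certainly governed what sites recorded.* Appendix 11 and the broader sentence in 9.2 say otherwise. If one of the two sites followed those, the second-year counts would depend on which passage it applied. That is a reason to reconcile the passages; it does not show that the tables are complete.

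**Conclusion.** The point holds. SAP 11.2.2 misdescribes collection after Month 12, against the specific rule in the protocol and against the SAP's own secondary endpoint. The distortion itself comes from the restricted collection combined with unsplit, unlabelled shells. In 14.3.1.3.1 the SAE, MAAE and study-withdrawal rows mix two collection rules and match no endpoint window. The all-AE counts in 14.3.1.3.2 to 14.3.1.3.5 share the mixed window.

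Under Protocol 9.2 the direction is fixed: all-cause totals can only be understated. The size cannot be derived from the documents. The restricted rule covers 46% to 50% of planned follow-up by group. The 14% to 48% range of missing events rests on assumed constant non-zero unrelated rates, no dropout and total loss of unrelated events after Month 12. The shortfall is zero if no such event occurs. Related SAE counts and percentages, and the AESI row, are not biased.

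**What to change.** 1. Rewrite the collection sentence in SAP 11.2.2 to the Protocol 9.2 rule: all SAEs, MAAEs and withdrawal AEs to Visit 15 (Month 12); related SAEs and MAAEs only after that; AESIs and intercurrent conditions throughout.
2. Reconcile Protocol Appendix 11 (Observation Period), and the sentence in 9.2 about documenting AEs over the entire trial, with that rule.
3. In 14.3.1.3.1, report all SAEs, all MAAEs and withdrawal AEs up to Visit 15. In separately labelled rows or tables for Month 12 to 24, report related SAEs, related MAAEs (a new row), AESIs and intercurrent conditions. This also supplies the windows that the SAE and MAAE endpoints in SAP 11.1 need.
4. Add a footnote to 14.3.1.3.2 to 14.3.1.3.5 giving the collection window of each event type, including the 28-day window for other unsolicited AEs.

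The cost is SAP wording, shell edits and the reconciling text. Event dates and relationship are already collected and appear in the AE listing, so no new data are needed.

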Repeat table 14.3.1.1.4.6 for related systemic solicited adverse events, categories: Temperature, Headache, Fatigue, Chills, Myalgia, Arthralgia, Nausea/ Vomiting and Diarrhea.

Sponsor

Clinical Study Report

Page x of y

Protocol number

14.3.1.2.1 Overall Summary of Unsolicited Adverse Events Within 28 Days After any Dose, Safety Analysis Set

Adverse Event Category [n (%) m]	CV7202 1 µg (N = xx)	CV7202 2 µg (N = xx)	CV7202 5 µg (N = xx)	Rabipur (N = xx)
All unsolicited adverse events	xx (xx.x%) xxx	xx (xx.x%) xxx	xx (xx.x%) xxx	xx (xx.x%) xxx
Related unsolicited adverse events	xx (xx.x%) xxx	xx (xx.x%) xxx	xx (xx.x%) xxx	xx (xx.x%) xxx
Serious adverse events	xx (xx.x%) xxx	xx (xx.x%) xxx	xx (xx.x%) xxx	xx (xx.x%) xxx
Related serious adverse events	xx (xx.x%) xxx	xx (xx.x%) xxx	xx (xx.x%) xxx	xx (xx.x%) xxx
Medically attended adverse events	xx (xx.x%) xxx	xx (xx.x%) xxx	xx (xx.x%) xxx	xx (xx.x%) xxx
Adverse events leading to withdrawal from study	xx (xx.x%) xxx	xx (xx.x%) xxx	xx (xx.x%) xxx	xx (xx.x%) xxx
Adverse events leading to discontinued vaccination	xx (xx.x%) xxx	xx (xx.x%) xxx	xx (xx.x%) xxx	xx (xx.x%) xxx
Adverse events of special interest	xx (xx.x%) xxx	xx (xx.x%) xxx	xx (xx.x%) xxx	xx (xx.x%) xxx

n = Number of subjects; m = Number of events; AEs on the day of vaccination and 28 subsequent days

Subjects reporting more than 1 event are counted only once for the subject count.

Percentages are based on total no. of subjects in each vaccination group.

Related: Adverse events which were assessed by the investigator as related to trial vaccine or study procedure.

PROGRAM SOURCE: tlf-###, DATA CUT OFF DATE: DDMMYYYY

RUN DATE: DDMMYYYY hh:mm

Programming note:

According to the SAP all unsolicited AE tables will be restricted to adverse events that occurred AFTER the first administration of the trial vaccine. If adverse events BEFORE are documented, these will be flagged and listed only.

Sponsor

Clinical Study Report

Page x of y

Protocol number

14.3.1.2.2 Overall Summary of Unsolicited Adverse Events Within 28 Days Post Dose 1, Safety Analysis Set

Adverse Event Category [n (%) m]	CV7202 1 µg (N = xx)	CV7202 2 µg (N = xx)	CV7202 5 µg (N = xx)	Rabipur (N = xx)
All unsolicited adverse events	xx (xx.x%) xxx	xx (xx.x%) xxx	xx (xx.x%) xxx	xx (xx.x%) xxx
Related unsolicited adverse events	xx (xx.x%) xxx	xx (xx.x%) xxx	xx (xx.x%) xxx	xx (xx.x%) xxx
Serious adverse events	xx (xx.x%) xxx	xx (xx.x%) xxx	xx (xx.x%) xxx	xx (xx.x%) xxx

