Related serious adverse events	xx (xx.x%) xxx	xx (xx.x%) xxx	xx (xx.x%) xxx	xx (xx.x%) xxx
Medically attended adverse events	xx (xx.x%) xxx	xx (xx.x%) xxx	xx (xx.x%) xxx	xx (xx.x%) xxx
Adverse events leading to withdrawal from study	xx (xx.x%) xxx	xx (xx.x%) xxx	xx (xx.x%) xxx	xx (xx.x%) xxx
Adverse events leading to discontinued vaccination	xx (xx.x%) xxx	xx (xx.x%) xxx	xx (xx.x%) xxx	xx (xx.x%) xxx
Adverse events of special interest	xx (xx.x%) xxx	xx (xx.x%) xxx	xx (xx.x%) xxx	xx (xx.x%) xxx

n = Number of subjects; m = Number of events;

AEs on the day of vaccination and 28 subsequent days, but before dose 2 CV7202 or dose 3 of Rabipur.

Subjects reporting more than 1 event are counted only once for the subject count.

Percentages are based on total no. of subjects in each vaccination group.

Related: Adverse events which were assessed by the investigator as related to trial vaccine or study procedure.

PROGRAM SOURCE: tlf-###, DATA CUT OFF DATE: DDMMYYYY

RUN DATE: DDMMYYYY hh:mm

Programming note:

According to the SAP all unsolicited AE tables will be restricted to adverse events that occurred AFTER the first administration of the trial vaccine. If adverse events BEFORE are documented, these will be flagged and listed only. AEs on the day of vaccination and 28 subsequent days, but before dose 2 CV7202 or dose 3 of Rabipur.

Sponsor

Clinical Study Report

Page x of y

Protocol number

14.3.1.2.3 Overall Summary of Unsolicited Adverse Events Within 28 Days Post Dose 2 CV7202 or Dose 3 Rabipur, Safety Analysis Set

Adverse Event Category [n (%) m]	CV7202 2x1 µg (N = xx)	CV7202 2x2 µg (N = xx)	Rabipur (N = xx)
All unsolicited adverse events	xx (xx.x%) xxx	xx (xx.x%) xxx	xx (xx.x%) xxx
Related unsolicited adverse events	xx (xx.x%) xxx	xx (xx.x%) xxx	xx (xx.x%) xxx
Serious adverse events	xx (xx.x%) xxx	xx (xx.x%) xxx	xx (xx.x%) xxx
Related serious adverse events	xx (xx.x%) xxx	xx (xx.x%) xxx	xx (xx.x%) xxx
Medically attended adverse events	xx (xx.x%) xxx	xx (xx.x%) xxx	xx (xx.x%) xxx
Adverse events leading to withdrawal from study	xx (xx.x%) xxx	xx (xx.x%) xxx	xx (xx.x%) xxx
Adverse events leading to discontinued vaccination	xx (xx.x%) xxx	xx (xx.x%) xxx	xx (xx.x%) xxx
Adverse events of special interest	xx (xx.x%) xxx	xx (xx.x%) xxx	xx (xx.x%) xxx

n = Number of subjects; m = Number of events;

AEs on the day of vaccination and 28 subsequent days

Subjects reporting more than 1 event are counted only once for the subject count.

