14.3.1.2.6 Unsolicited Adverse Events Within 28 Days Post Dose 1, Safety Analysis Set

System organ class Preferred term [n (%) m]	CV7202 (N = xx)	CV7202 (N = xx)	CV7202 (N = xx)	Rabipur (N = xx)	Total (N = xx)
Any adverse events	xx (xx.x%) xxx	xx (xx.x%) xxx			
System organ class 1	xx (xx.x%) xxx	xx (xx.x%) xxx			
Preferred term 1	xx (xx.x%) xxx	xx (xx.x%) xxx			
Preferred term 2	xx (xx.x%) xxx	xx (xx.x%) xxx			
Preferred term 3	xx (xx.x%) xxx	xx (xx.x%) xxx			
Preferred term 4	xx (xx.x%) xxx	xx (xx.x%) xxx			
...	xx (xx.x%) xxx	xx (xx.x%) xxx			
System organ class 2	xx (xx.x%) xxx	xx (xx.x%) xxx			
Preferred term 1	xx (xx.x%) xxx	xx (xx.x%) xxx			
Preferred term 2	xx (xx.x%) xxx	xx (xx.x%) xxx			
Preferred term 3	xx (xx.x%) xxx	xx (xx.x%) xxx			
...	xx (xx.x%) xxx	xx (xx.x%) xxx			

n = Number of subjects; m = Number of events;

AEs on the day of vaccination and 28 subsequent days, but before 2nd CV7202 or 3rd Rabipur vaccination.

Adverse events were coded using MedDRA version 24.1. At each level of summation (system organs class, preferred term) subjects reporting more than 1 event are included only once.

Table is sorted by descending subject count in the total column by system organ class and preferred term.

Percentages are based on total number of subjects in each vaccination group

PROGRAM SOURCE: tlif-###, DATA CUT OFF DATE: DDMMYYYY

RUN DATE: DDMMYYYY hh:mm

Programming note:

Sort by decreasing frequency of the total column by SOC and preferred term.

According to the SAP all unsolicited AE tables will be restricted to adverse events that occurred AFTER the first administration of the trial vaccine (post vaccination). If adverse events BEFORE are documented, they will be flagged and listed only.

Sponsor

Clinical Study Report

Protocol number

Page x of y

14.3.1.2.7 Unsolicited Adverse Events Within 28 Days Post Dose 2 CV7202 or Dose 3 Rabipur, Safety Analysis Set

System organ class Preferred term [n (%) m]	CV7202 2x1 µg (N = xx)	CV7202 2x2 µg (N = xx)	Rabipur (N = xx)	Total (N = xx)
Any adverse events	xx (xx.x%) xxx	xx (xx.x%) xxx	xx (xx.x%) xxx	xx (xx.x%) xxx
System organ class 1	xx (xx.x%) xxx	xx (xx.x%) xxx	xx (xx.x%) xxx	xx (xx.x%) xxx
Preferred term 1	xx (xx.x%) xxx	xx (xx.x%) xxx	xx (xx.x%) xxx	xx (xx.x%) xxx
Preferred term 2	xx (xx.x%) xxx	xx (xx.x%) xxx	xx (xx.x%) xxx	xx (xx.x%) xxx
Preferred term 3	xx (xx.x%) xxx	xx (xx.x%) xxx	xx (xx.x%) xxx	xx (xx.x%) xxx

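### The day numbers in SAP 11.2.2 for assigning unsolicited AEs to doses conflict with the SAP's own dose-date rule and can miscount the by-dose tables

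*SAP*

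**What the plan says.** SAP 11.2.2 opens its allocation rule with a sentence tied to the injection: "Every unsolicited AE will be assigned to a vaccination dose (number) by consideration of the period of 28 days after vaccination administration". It then gives day numbers: "Unsolicited AEs can be assigned to either day 1 to 28 (dose 1 for any vaccination group), or day 29 to 57". The second range is for Dose 2 of the two-dose regimens or Dose 3 of Rabipur. Rabipur Dose 2 is given no AEs of its own.

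The primary endpoint in SAP 11.1, which matches protocol 4.2, counts "unsolicited and related unsolicited AEs reported on the day of vaccination and the 28 subsequent days (Days 1-29"), that is, 29 days. SAP 11.2.2 repeats that window for presentation: "The occurrence of unsolicited AEs reported on the day of vaccination and the 28 subsequent days will be presented".

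The table shells carry a third statement. The any-dose overview, 14.3.1.2.1, uses "AEs on the day of vaccination and 28 subsequent days". The post-Dose-1 overview, 14.3.1.2.2, uses "AEs on the day of vaccination and 28 subsequent days, but before dose 2 CV7202 or dose 3 of Rabipur". The post-Dose-1 table by system organ class and preferred term, 14.3.1.2.6, uses "AEs on the day of vaccination and 28 subsequent days, but before 2nd CV7202 or 3rd Rabipur vaccination".

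**The concern.** A programmer who follows the day numbers and one who follows the footnotes will fill the same by-dose tables differently. Two situations expose the difference.

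- **One-dose subjects.** They have no later dose, so nothing should close their Dose 1 window before Day 29. Protocol 9.4.6 and 9.4.9 have them record unsolicited AEs to Day 29 as Dose 1 data.
- **Subjects whose Day 29 dose is given on another day.** Fixed days can then place AEs that began before the injection under that injection, and cut off the end of its follow-up.

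Tolerability after one dose versus two bears on the trial's stated aim of choosing the dose and the number of doses. Each two-dose column has only 8 planned subjects, so single events are visible in it.

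**Working it through.** **Inputs**

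- Literal rule (SAP 11.2.2): Dose 1 = Days 1-28 for every group; later dose = Days 29-57.
- Dose-date rule (shells 14.3.1.2.2 and 14.3.1.2.6 for Dose 1; 14.3.1.2.3 and 14.3.1.2.7 for the later dose): vaccination day plus 28 days, with Dose 1 cut at CV7202 Dose 2 or Rabipur Dose 3.
- Group sizes (protocol Table 8.1 and 8.5): 10 subjects at 5 µg with one dose; 16 at 1 µg and 16 at 2 µg, 8 of each with a second dose.
- Window for the Day 29 visit (protocol Table 2.1, read by column position): +/-2 days, so Days 27-31.
- Minimum interval between CV7202 doses (protocol 5.2, SAP 4): 28 days, so Day 1 + 28 = Day 29 at the earliest.

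**Can one rule give both stated ranges?**

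- Vaccination day plus 28 days: 29 + 28 = 57 reproduces the later range, but 1 + 28 = 29 does not give Day 28.
- 28 days counting the vaccination day: Days 1-28 is reproduced, but the later range becomes Days 29-56.
- Vaccination day plus 28 days, cut at a later dose on Day 29: this gives Days 1-28 and 29-57, but only for subjects who receive a later dose. The SAP applies Day 28 to every group.

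No single rule gives both ranges for all groups.

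**One-dose subjects**

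10 + 8 + 8 = 26 of 42 planned CV7202 subjects. A Day 29 AE lies inside the 29-day endpoint window. The literal rule excludes it from Dose 1, and the later-dose shells 14.3.1.2.3 and 14.3.1.2.7 have columns only for 2x1 µg, 2x2 µg and Rabipur. The AE therefore appears in the any-dose tables and in neither by-dose set, although the lead sentence says every AE is assigned to a dose. The day at issue is 1 of 29, or 3.4% of the window. That is a share of days, not of events.

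**Subjects with a later dose on Day D**

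| D | Dose-date window, D to D + 28 | Where the literal rule differs |
|---|---|---|
| 29 | 29-57 | No day |
| 30 | 30-58 | Day 29 (pre-dose) goes to the later dose; Day 58 is lost |
| 31 | 31-59 | Day 29 (Dose 1 window) and Day 30 (in neither window) go to the later dose; Days 58-59 are lost |
| 28 | 28-56 | Day 28 (vaccination day) goes to Dose 1; Day 57 is counted although outside |
| 27 | 27-55 | Days 27-28 go to Dose 1; Days 56-57 are counted although outside |

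The largest disagreement is 4 calendar days per subject. For CV7202, the last two rows fall within the visit window but breach the minimum interval. The sentence that sets that interval gives none for Rabipur.

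**The case against.** The strongest reply is that the SAP already has the right rule. The lead sentence of 11.2.2 is anchored on administration, and the day numbers can be read as shorthand for the nominal schedule. The post-Dose-1 footnotes already keep Day 29 for one-dose subjects and already stop at the actual later dose. On that reading nothing is misassigned. This limits the point: the error arises only if the day numbers are programmed as written, and a reader who infers that the SAP fixes allocation by calendar day regardless of dosing date goes further than the text. It does not remove the point, because one section gives two rules. The nominal reading also does not rescue Day 28 for groups that have no Day 29 dose.

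A reader might also infer that the rule contradicts or shortens the primary endpoint. The documents do not support that. The endpoint needs no allocation by dose number, and the any-dose shells 14.3.1.2.1, 14.3.1.2.4 and 14.3.1.2.5 keep the full window, so no Day 29 AE leaves them.

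Two further limits stand. When the later dose is given on Day 29, that day belongs to both windows, and giving it to the later dose is a necessary tie-break. And early dosing on Days 27-28 cannot be treated as simply permitted for CV7202 while the minimum interval says otherwise.

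**Conclusion.** The point holds as an internal inconsistency of the SAP that affects the by-dose unsolicited AE tables only. The one-dose part needs no assumption about dosing dates: for 26 of 42 planned CV7202 subjects, the stated Dose 1 range is one day short of the SAP's own window. The off-day part assumes that the day numbers are programmed literally and that some later doses fall off Day 29. Dosing on Day 30 or 31 then moves one or two pre-dose days to the later dose and drops one or two days from its end.

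The effect on reported percentages cannot be calculated, because the documents give neither the number of off-day doses nor AE onset dates. It is tempting to quote a shift of 12.5 points (1/8) in a two-dose column. That is the effect of one hypothetical subject whose only AE in that row and window falls on a boundary day after an off-day dose. It is not an expected size.

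**What to change.** Replace the day numbers in SAP 11.2.2 with the dose-date rule already in the shells:

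- An AE is assigned to a dose if its onset is on the day of that dose or within the 28 days after it, and before CV7202 Dose 2 or Rabipur Dose 3 where given.
- One-dose subjects keep Day 29 under Dose 1.
- An AE on the day of the later dose goes to the later dose.
- An AE that falls between the Dose 1 window and the later dose is assigned to neither. In a CV7202 subject it appears only in the whole-trial tables (14.3.1.3.x). In a Rabipur subject it also stays in the any-dose 28-day tables, because the nominal window of Rabipur Dose 2 runs to 8 + 28 = Day 36.

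Use the same wording in the footnotes of all by-dose 14.3.1.2.x shells. The cost is a text edit: vaccination dates are already collected and listed (SAP 11.3, listing 16.2.5), and no new data are needed.

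Separately, the +/-2-day window for Day 29 in protocol Table 2.1 and the minimum interval between CV7202 doses in protocol 5.2 and SAP 4 must be reconciled. This review does not say which should prevail.
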